patient data, patient's name, hospital name, and medical record number will not be entered into the system. For clinical diagnoses of the study recipients, descriptive diagnoses, including ICD-9 codes will be entered into the Data Forms by the coordinator at each Center. The REDS-II Center's staff will manually record data into the Data Forms and mail them to the Coordinating Center for coding and data entry. The data from the web based system and the Data Forms will eventually be compiled into a single dataset for analysis.

F20. Standardized protocol for donors/recipients testing for cases of TRALI identified in the study: The basic requirement for the protocol would be to test all involved donors for HLA and HNA antibodies as described above for LAPS donors. Depending upon hospital's cooperation for case investigation, recipient testing for HLA and HNA antibody, HLA and HNA phenotyping will be pursued, but not required. . Because it is difficult to coordinate sample acquisitions on donors and recipients simultaneously, crossmatch between donor serum and recipient leukocytes will not be performed.

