A list of the components that were supplied to each participating hospital will then be printed by the blood center and provided to each corresponding transfusion service medical director or designated individual to identify corresponding recipients and to have the radiology and the medical records be abstracted by the record review coordinator(s). All information will be tracked and compiled into the tracking and data management systems either directly by research staff at the blood center/blood bank or by Westat, if forms are mailed to the coordinating center for data entry.

The coordinating center will be responsible for formation of the medical review board. The medical review board will assess all completed data forms in a blinded manner to determine the presence or absence of TRALI as described above. The coordinating center will compile the results of these reviews into the data management system to allow for formation of a database that will be used for analyses. The proposed diagnostic criteria for TRALI are detailed in the next section.

F25. Proposed Diagnostic criteria for TRALI: Using the Canadian Consensus Conference criteria, the medical review board will be responsible for reviewing the completed recipient forms and determining the presence or absence of TRALI (Kleinman et al).

- 1. New hypoxemia must be present and hypoxemia is defined as pO2/FiO2 ratio of <300 within 6 hours of completion of transfusion or venous oxygen saturation (SpO2) of less than 90% on room air; or other clinical evidence of hypoxemia (e.g., cyanosis). Based on the recent report from Rice TW et al., additional criteria to determine hypoxemia representative of ARDS will be included as follows: ratio of SpO2/FiO2 <315; where FiO2 will be calculated for patients receiving oxygen by cannula or mask as follows: 1 liter = 0.21; 2 liters = 0.23; 3 liters = 0.25; 4 liters = 0.3; 5 liters = 0.35; 6 and 7 liters = 0.45, and 8,9, and 10 liters = 0.49 (Rice TW 2007).
- 2. Bilateral infiltrates on frontal chest radiograph (obtained within 24 hours of Completion of transfusion) must be present. There must be absence of left atrial hypertension (i.e., circulatory overload). However, if ALI is diagnosed by the expert panel in the presence of left atrial hypertension, the case may be classified as TRALI/TACO (overlap case).

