- 3. For definition of left atrial hypertension, one or more of the following criteria must be present: EKG evidence for recent MI, echocardiogram indicative of heart failure or an ejection fraction <50%, a plasma troponin value greater than the upper reference range of the laboratory, a plasma brain natriuretic peptide of >100 pg/mL, pulmonary edema fluid/plasma fluid protein ratio less than 0.60, and pulmonary artery diastolic pressure or pulmonary artery wedge pressure of 18 mm Hg or more.

In addition to the above, clinical criteria for congestive heart failure, e.g., elevated jugular venous pressure, presence of S3 and S4 sound on auscultation, hepatojugular reflux, and excess input of fluid compared to output, and response to diuretic will be considered in order to differentiate TACO from TRALI.

- 4. No pre-existing acute lung injury before transfusion
- 5. No temporal relationship to an alternate risk factor for acute lung injury
 - Note: Recipients who meet the above criteria but also have a clear relationship to an alternate risk factor for acute lung injury will be considered to have possible TRALI. Also, in accordance with the NHLBI definition, such cases will be classified as TRALI with other risk factors for acute lung injury, provided that the expert panel determines that transfusion is the most likely cause of the ALI. ALI risk factors could be those that cause direct lung injury or those that cause indirect lung injury. Factors that cause direct lung injury are: aspiration, pneumonia, toxic inhalation, lung contusion, and near drowning. Factors that cause indirect lung injury are severe sepsis, shock, multiple trauma, acute pancreatitis, cardiopulmonary bypass, and drug overdose.

6. If the chest x-ray report review indicates absence of bilateral pulmonary infiltrates, the cases will be designated as "Not TRALI".

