3	PLATELETS, APHERESIS (No. of Units)		
4	PLASMA (No. of Units)		
5	CRYSTALLOIDS - Normal saline, Half normal saline, D5W, D5/Half Normal saline, Lactated Ringer's solution (mL)		
6	COLLOIDS - albumin, plasma protein fraction or PPF (mL)		
7	Urine output (mL)		
8	Gastric tube output (mL)		
9	Surgical drain output (mL)		
10	Fluid balance – Excess fluid (mL)		

SECTION L: ELECTROCARDIOGRAM FINDINGS

PRE-TRANSFUSION EKG REPORT (Please write complete reports in box below for all EKGs that were done within 24 hrs prior to study unit transfusion. Please write date/time for each report.)

POST-TRANSFUSION EKG REPORT (Please write complete reports in box below for all EKGs that were done within 24 hrs after study unit transfusion. Please write date/time for each report.)

SECTION M: ECHOCARDIOGRAM FINDINGS (M-MODE & 2-D)

PRE-TRANSFUSION ECG WRITTEN REPORT (Please write complete report in box below; if more than one report, include all reports. Please write date/time for each report.)

POST-TRANSFUSION ECG WRITTEN REPORT (Please write complete report in box below; if more than one report, include all reports. Please write date/time for each report.)

SECTION N: LABORATORY FORM

COM	PLETE BLOOD COUNT	[
NO.	PARAMETER	PRE-Tx (Most recent within 24 hrs. Record if applicable)			POST-Tx (Most recent within 24 hrs. Record if applicable)		
		DATE	TIME (military)	VALU E	DAT E	TIME (military)	VALU E
1	Hemoglobin gm/dL						
2	Hematocrit (%)						
3	Total WBC x 10 ³ /uL						
4	Monocytes (%)						
5	Neutrophil (%)						
6	Lymphocyte (%)						
7	Platelet count x 10 ³ /uL						

OTHER LAB RESULTS

			PRE-Tx (Most recent within 24 hrs. Record			POST-Tx		
				rs. Record		recent within		
NO.	PARAMETER	if	if applicable)			Record if applicable)		
		DATE	TIME (military)	VALUE	DATE	TIME (military)	VALUE	
1	BUN (mg/dL)							
2	Creatinine (mg/dL)							
3	CK (IU/L)							
4	CK-MB (IU/L)							
5	Troponin I (IU/L)							
6	K (mEq/L)							
7	Na (mEq/L)							
8	B-type natriuretic peptide (pg/mL)							
9	Fibrinogen level (mg/dL)							
10	Fibrin degradation, d- dimer, or split products (record value)							
11	Total bilirubin (mg/dL)							

SECTION O: ARTERIAL BLOOD GASES

Record all values within six hours of the study unit transfusion

	DATE	TIME	FiO ₂	PaO ₂	PaCO ₂	pН
PRE-Tx						
(Most recent within 6 hrs)						
POST-Tx						
Closest to time of reaction						
(Not more than 11 hrs and 59						
min after completion of Tx)						
POST-Tx						

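### The Appendix G form does not let the board fully apply the F25 test for left atrial hypertension: troponin has no laboratory limit, two markers have no field, the wedge-pressure cut-off differs, and laboratory timing is loose

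*Protocol*

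**What the plan says.** F25, item 2 makes the absence of left atrial hypertension a condition of TRALI: "There must be absence of left atrial hypertension (i.e., circulatory overload". It also lets the expert panel class a case as TRALI/TACO overlap if acute lung injury is diagnosed although left atrial hypertension is present.

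F25, item 3 sets an any-one rule: "one or more of the following criteria must be present". Counting the two pulmonary artery pressures separately, it lists seven markers:

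- EKG evidence of recent infarction
- echocardiogram showing heart failure or an ejection fraction below 50%
- "a plasma troponin value greater than the upper reference range of the laboratory"
- BNP above 100 pg/mL
- "pulmonary edema fluid/plasma fluid protein ratio less than 0.60, and pulmonary artery diastolic pressure" (two markers), the diastolic pressure counting from 18 mm Hg
- wedge pressure, also from 18 mm Hg

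Clinical signs such as jugular pressure, fluid balance and response to diuretic are weighed in addition.

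On the source of the decision, F25 says that "the medical review board will be responsible for reviewing the completed recipient forms". In Appendix G, Section N the troponin line reads "Troponin I (IU/L" and has columns for date, time and value. The post-transfusion column is headed "POST-Tx (Most recent within 24 hrs. Record if applicable". Section O, on blood gases, instead asks first for the post-transfusion sample nearest the time of reaction, and Note 21 defines when the reaction occurred. F19 states for recipient data that "patient's name, hospital name, and medical record number will not be entered into the system".

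**The concern.** When any one marker is enough, absence can be confirmed only if every marker that was measured reaches the reader. A marker that was measured but has no place on the form, or that was replaced by a later and lower value, looks the same as a negative one. TACO is the main competing diagnosis: F5 expects triage to remove perhaps 50% of the 311 charts as TACO, about 155, against 40 projected TRALI cases (F26). The triage section of the form removes a case only when the evidence of TACO is clear, so the less clear cases, where a single marker may decide, go to the board.

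An overload case that loses its deciding marker could be classed as TRALI instead of TACO or TRALI/TACO. The readers are blinded to antibody status, so such errors should fall on both arms alike. They would raise both rates by a similar amount, lower the ratio and cost power.

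**Working it through.** **Step 1. Each F25, item 3 marker against Appendix G.**

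| F25 marker | Appendix G | Can the criterion be applied? |
|---|---|---|
| EKG, recent infarction | Section L: full reports, 24 h before and after | Yes |
| Echocardiogram, heart failure or EF <50% | Section M: full reports | Yes |
| Troponin above the laboratory's limit | Section N: troponin I, one unit, value only | Not without the limit or a flag |
| BNP >100 pg/mL | Section N: numeric, pg/mL | Yes, for the one value recorded |
| Protein ratio <0.60 | No field | No |
| Pulmonary artery diastolic pressure ≥18 mm Hg | No field | No |
| Wedge pressure ≥18 mm Hg | Sections H and J: yes/no/NR at >20 mm Hg, within 6 h | Not for 18 to 20 mm Hg |

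Three of the seven can be applied, one lacks its reference limit, two have no field, and one is captured at a different cut-off. Of the supporting signs, S3/S4 has no field. Jugular pressure, hepatojugular reflux, fluid balance and response to diuretic do.

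**Step 2. Timing.** Section N keeps one post-transfusion value per analyte. Read literally, the most recent value within 24 hours is the last one in the window. A troponin or BNP that was raised near onset and had fallen later would be recorded only at its later level. EKG and echocardiogram are not affected, because all reports are transcribed. F25 sets no sampling window for the markers, so this is an ambiguity in the form and not a contradiction with F25.

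**Step 3. Which cases are exposed.** Only those whose sole positive marker is troponin, the protein ratio, pulmonary artery diastolic pressure or a wedge pressure of 18 to 20 mm Hg, or whose only positive troponin or BNP came earlier than the value recorded. The documents do not say how many there would be.

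**Step 4. Illustration of the effect.** Inputs from Appendix D: 2.32% in case recipients, 0.79% in controls, 1,175 per arm, one-sided 0.05 level, exact test.

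- Planned ratio: 2.32 / 0.79 = 2.94. Power of the one-sided Fisher test by exact enumeration: 90.0%, which reproduces the stated 90%.
- Assume that overload cases equal to a share d of recipients are called TRALI in each arm. The ratio becomes (2.32 + d) / (0.79 + d). The difference stays at 2.32 − 0.79 = 1.53 percentage points, but the variance rises.

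| d (assumed) | Recipients per arm, of 1,175 | Ratio | Power |
|---|---|---|---|
| 0 | 0 | 2.94 | 90.0% |
| 0.1% | 0.001 × 1,175 = 1.2 | 2.42 / 0.89 = 2.72 | 88.1% |
| 0.3% | 0.003 × 1,175 = 3.5 | 2.62 / 1.09 = 2.40 | 84.2% |
| 0.5% | 0.005 × 1,175 = 5.9 | 2.82 / 1.29 = 2.19 | 80.4% |

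The values of d have no source in the documents.

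**The case against.** The strongest reply is that this is expert adjudication and not an algorithm run on form fields. Two blinded readers judge each case and confer if they disagree (F21). The reviewers also receive a slide summary, and images where available. Several routes to recognising overload are well captured: EKG, echocardiogram, BNP, jugular pressure, fluid balance, weight loss after diuretic, and rapid clearing of infiltrates. This stands, and it limits the point. A reader might infer that left atrial hypertension cannot be determined from the form at all. It often can, because any one of the captured markers is enough. What the form does not support is confirming absence on all seven.

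A reader might also infer from F19 that the troponin limit is lost because the hospital name is withheld. The documents do not support that. F12B records the receiving hospital for each component, Appendix G carries the blood unit identifier, and the coordinator's link is kept until the end of the study (F18). The limit could be queried during the study, but no step provides for it.

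Nor does one positive marker necessarily take a case out of the TRALI group, since F25, item 2 allows the overlap class. White cell and neutrophil counts share the timing rule, but they are not an F25 criterion and cannot change this classification.

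Finally, the column header over troponin and BNP is broken in the extracted text; its wording is read from the intact blood-count table above it. Abstraction instructions may also sit in the Manual of Procedures, which is not at hand. That could settle how the most recent value is to be read, but it would not add the missing fields or align the wedge cut-offs.

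**Conclusion.** The point holds in a limited form. Appendix G does not let the board fully apply F25, item 3, because four of the seven markers are missing, lack their reference limit or are captured at a different cut-off, and the timing rule for laboratory values can pass over the value near onset. The wedge-pressure mismatch is a direct inconsistency, and the passages must be reconciled.

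The size is not known. It is bounded by the cases positive only on an uncaptured marker or only on an earlier troponin or BNP, which is some part of the at most 311 full reviews. The illustration, a ratio of 2.72 to 2.19 and power of 88.1% to 80.4%, rests on assumed rates of 0.1% to 0.5% and on error that is equal in both arms and runs only from overload to TRALI. Under those conditions the effect is dilution. The documents give no ground for inferring that it would produce a false difference between the arms. This is a cheap improvement to data capture and does not invalidate the primary comparison.

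**What to change.** Revise Appendix G before data collection:

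- In Section N, record the troponin type, its unit, and the laboratory's upper limit or its high flag.
- Add fields for pulmonary artery diastolic pressure and for the edema-fluid/plasma protein ratio.
- Record wedge pressure as a number, and reconcile the cut-offs in F25 and Appendix G.
- For post-transfusion BNP and troponin, replace the most recent value by the one closest to onset as defined in Note 21, plus the highest within 24 hours, each with its time.

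The cost is a form revision and a few more values copied per reviewed chart, for about 311 charts. No new tests are needed, since everything asked for is existing chart data where it was measured. Making the change before abstraction begins avoids going back to charts already reviewed.

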NO.	ITEM	YES	NO	NR	NOTES
22	Hx of leukemia or lymphoma				
23	Lung contusion during current admission (if diagnosis made within 48 hrs before reaction)				Note 11
24	Lung radiation in previous six months				
25	Multiple fractures during current admission (Within 7 days before Tx)				
26	Near drowning as reason for admission (within 48 hrs before reaction)				
27	Hx of chronic obstructive lung disease				
28	Acute pancreatitis during current admission (within 7 days before Tx)				Note 12
29	Rapid resolution of lung infiltrates on chest x-ray				If within 6 hrs with diuresis/ dialysis
30	Receiving amiodarone during current admission (within 48 hrs before reaction)				
31	Hx of restrictive lung disease				
32	Hx of severe liver disease				Note 13
33	Symptomatic anemia during current admission (within 48 hrs before reaction)				Note 14
34	Upper airway obstruction during current admission (within 48 hrs before reaction)				

SECTION G: OTHER CLINICAL FINDINGS

NO.	ITEM	YES	NO	NR	VALU E	DATE	TIME (military)	NOTES
1	Dialysis within 7 days before the study unit Tx (Hemo or Peritoneal)							
2	Dialysis within 7 days after the study unit Tx (Hemo or Peritoneal)							
3	Extubation (within 24 hrs before reaction)							Note 15
4	FiO2 (highest value) in 24 hrs before Tx of study unit							
5	FiO2 (highest value) in 24 hrs after Tx of study unit							
6	Fluid balance – Excess fluid 24 hrs before Tx of study unit (mL)							Note 16
7	Intubation within 24 hrs before Tx of study unit							
8	Intubation within 24 hrs after Tx of study unit							

9	Invasive procedure: Central line placement within 24 hrs before Tx.							
---	---	--	--	--	--	--	--	--

NO.	ITEM	YES	NO	NR	VALU E	DATE	TIME (military)	NOTES
10	Invasive procedure: Liver biopsy							
11	Invasive procedure: Lumbar puncture (within 24 hrs before Tx.)							
12	Invasive procedure: Other (within 24 hrs before Tx.) Specify							
13	Mechanical ventilation within 24 hrs before study unit Tx							
14	List all medications given to the	patient w	ithin 2	4 hrs p	rior to trans	fusion:		

NO.	ITEM	PROCEDUR	E	DATE	TIME (military)	NOTES
		Nasal Cannula				
15		Face Mask				
	Oxygen administration method within 24 hrs before Tx of study unit	СРАР				
		Intubation				
		Other				
		Nasal Cannula				
		Face Mask				
16	Oxygen administration method within 24 hrs after Tx of study unit	СРАР				
		Intubation				
		Other				

SECTION H: PRE-TRANSFUSION EVENTS

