**** END ****

NOTES

Note 1: All post-transfusion vital signs may not have been recorded. Complete those that are in the medical record.

Note 2: Describe the type of reaction. Following are the possible types of reactions: Febrile non-hemolytic transfusion reaction, allergic skin reaction, acute hemolytic transfusion reaction, delayed hemolytic transfusion reaction, bacterial sepsis, shock, anaphylaxis, cardiac overload, hypotension, shock, transfusion-associated dyspnea (TAD), tachycardia, tachypena (respiratory rate >22/minute, chills, fever, shortness of breath, circulatory overload, back pain, sweating, nausea, vomiting, hyperbilirubinemia, etc.

Note 3: The types of CNS injuries include sub arachnoid hemorrhage, subdural hematoma, closed head injury and stroke. Include only if the injury occurred within seven days prior to the study unit transfusion.

Note 4: If noted in medical records, or if <500 mL urine output in 24 hours or new elevated creatinine of >1.5 mg/dL.

Note 5: Select "yes" if aspiration event was witnessed and documented in the medical record. Select "no" if aspiration was suspected but not witnessed.

Note 6: Greater than 3 drinks on 5 or more days a week for males; greater than 2 drinks on 5 or more days a week for females or if documented in medical record.

Note 7: Chronic creatinine >1.5 mg/dL.

Note 8: Select "yes" if medical record indicates history of CHF or CHF present before transfusion during current admission. Select "Yes" if echocardiogram shows ejection fraction less than 40% or shows diastolic dysfunction or if there is cardiomegaly on chest x-ray.

Note 9: Diabetes can be either type I (insulin-dependent) or type-II (non-insulin-dependent).

Note 10: Select "yes" if MD note indicates presence of DIC or if platelet count <100,000/uL + fibrin degradation products or if platelet count <100,000/uL + fibrinogen concentration <100 mg/dL.

Note 11: Select "yes" if patient has lung infiltrate/s on chest x-ray within 8 hours of admission to the emergency room and has evidence of blunt trauma to the chest noted in medical record or has rib fracture/s or was involved in motor vehicle accident.

Note 12: Select "yes" if within 7 days before transfusion.

Note 13: If medical record indicate any one or more of the following: biopsy proven cirrhosis, portal hypertension, or past episodes of upper GI bleeding attributed to portal hypertension, prior episodes of liver failure/enechalopathy/coma.

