Note 14: If patient received any RBC transfusion for drop in hemoglobin or hematocrit, select "yes".

Note 15: Extubation date/time should be recorded when the extubation is performed and note that this time may occur beyond the 24-48 hours after the transfusion. If intubation was performed and extubation did not take place (e.g. patient was discharged to a chronic ventilatory care facility while intubated), record No. If no record exists to determine the date/time of intubation, record NR.

Note 16: Calculate the excess fluids administered by fluids given (oral or intravenous) minus fluid losses (urine, gastric suction, thoracic or abdominal drainaige) in 24 hours prior to the transfusion. Write down the amount of excess fluid in mL.

Note 17: Pre-transfusion bacterial sepsis: If MD or nursing note indicates possibility of sepsis or a diagnosis of sepsis; other manifestations include a focus of infection (e.g. pneumonia, cellulitis, skin lucer, wound infection); manifestations of inflammation (e.g. fever, tachycardia, tachypnea), and shock (BP less than 90 mmHg systolic; sweating, cold clammy skin). Laboratory test may also show positive blood culture.

Note 18: Pre-transfusion shock: MD or nursing note indicating presence of shock. Manifestations include low systolic BP (<90 mmHg), tachycardia, cold clammy skin, distal extremity cyanosis, low urine output, mental confusion or somnolence.

Note 19: Calculate ratio by dividing the percent saturation of oxygen on pulse oxy (SO2) by FiO2 (calculate FiO2 as follows: room air = 0.21; one liter oxygen = 0.23; 2 liters = 0.25; 3 liters = 0.27; 4 liters = 0.3, 5 liters = 0.35; 6 & 7 liters = 0.4; and 8-10 liters = 0.49. Example: If oxygen saturation is 90% on 4 liters of oxygen by face mask, then the ratio is 90/0.3 = 300.

Note 20: PF ratio. Calculate by dividing the pO2 (on arterial blood gases) by FiO2 (flow rate of oxygen in decimel of 1.0, e.g., 40% FiO2 = 0.4). Example: Someone with pO2 of 120 receiving 40% oxygen, the PF ratio is $120 \div 0.4 = 300$.

Note 21: The definition of when the reaction occurred is the earliest time at which one or more of the following events were noted: pO2/FiO2 <300; SO2/FiO2 <315, and pulmonary edema on chest x-ray.

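### The extended form has no dated item for two of the five direct lung-injury factors in F25 and codes suspected aspiration as absent, so these factors may be under-recorded

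*Protocol*

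**What the plan says.** Protocol F25, item 5, lists the alternate causes that separate TRALI from possible TRALI (Canadian definition) and from TRALI with other risk factors (NHLBI definition). For direct injury it says: "Factors that cause direct lung injury are: aspiration, pneumonia, toxic inhalation, lung contusion, and near drowning". A case with such a factor stays in the TRALI group only if the panel judges transfusion the most likely cause. G2 states that the data collection form will allow classification under both definitions.

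The form in question is Appendix G. Section F of that form has "Lung contusion during current admission (if diagnosis made within 48 hrs before reaction") as item 23 and "Near drowning as reason for admission (within 48 hrs before reaction") as item 26. Aspiration is item 3, governed by Note 5, which reserves *yes* for a witnessed, documented event and calls for *no* "if aspiration was suspected but not witnessed". Pneumonia appears only in Note 17, which explains the pre-transfusion bacterial sepsis item: "other manifestations include a focus of infection (e.g. pneumonia, cellulitis, skin lucer, wound infection"). Toxic inhalation appears nowhere on the form; the nearest item is burn as an admitting diagnosis (item 5).

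C1 includes cases with other risk factors in the primary definition of TRALI. Section L plans separate incidences for TRALI without and with other risk factors, and Appendix I gives each its own column.

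**The concern.** The form does not carry the protocol's own criteria through to data collection. F25 asks whether ALI is related in time to one of the listed factors. For two of the five direct factors the abstractor is never asked, and for a third a charted suspicion is entered as an explicit negative even though the form has a not-recorded column. Saving space does not explain the gap, since Section F has rows for heat stroke and high altitude.

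At stake is the breakdown by risk factor. A case whose only alternate factor is an unprompted pneumonia, an inhalation injury or an unwitnessed aspiration could be placed under TRALI without other risk factors, or under TRALI rather than possible TRALI in the Canadian scheme. A second route is narrower: if the panel never sees the factor, it has no reason to ask whether transfusion was the most likely cause, and an ALI case could be counted as TRALI.

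**Working it through.** **1. Match F25 to the form.**

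| F25 factor | Item in Appendix G |
|---|---|
| Aspiration | Section F item 3; suspected events coded *no* (Note 5) |
| Pneumonia | None; an example within Note 17 (sepsis, Section H item 3) |
| Toxic inhalation | None |
| Lung contusion | Section F item 23 |
| Near drowning | Section F item 26 |
| Severe sepsis | Section H item 3 |
| Shock | Section F item 18, Section H item 7 |
| Multiple trauma | Nearest is multiple fractures, Section F item 25 |
| Acute pancreatitis | Section F item 28 |
| Cardiopulmonary bypass | Section F item 7 |
| Drug overdose | Section F item 15 |

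Two of five direct factors have no item and one of five has a restrictive code. All six indirect factors have an item or a close one. Section F is numbered 1 to 34 without a gap, so the absence is not an artefact of text extraction.

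**2. Other routes to the panel.**

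- Slide summary of events and timeline (F4). Free text; content depends on the coordinator.
- Verbatim chest x-ray reports with date and time (F3, Appendix F). Pre-transfusion films only where they exist.
- Up to ten discharge diagnoses with codes (Appendices F and G). No onset date.
- Sepsis item with Note 17. Pneumonia entered here is recorded as sepsis, which F25 lists as an indirect factor and only when severe.
- Indirect clues: fever, rales and rhonchi (Section H), medications in the prior 24 hours (Section G item 14), white cell counts (Section N).

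The factors are therefore obtainable, but no route prompts for them in a uniform, dated way.

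**3. Which analyses are touched.** The split in Section L depends directly on these data, and under-recording moves cases one way, toward the class without risk factors. The primary count is the sum of the two classes (C1), so moving a case between them leaves it unchanged. It changes only if a missed factor would have turned the panel's answer from TRALI to ALI.

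**4. Illustration for the primary test.** Inputs from Appendix D: 2.32% versus 0.79%, 1,175 per group, one-sided 0.05 exact conditional test, stated power 90%. Reject when the hypergeometric tail P(X ≥ x | total m) ≤ 0.05. Power is the sum of Bin(x; 1175, p1) × Bin(m − x; 1175, p2) over the rejection region. This reproduces the plan's figure: 90.0%.

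Now add the same false-TRALI rate f to both groups. The values of f are assumptions; the protocol gives none.

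| f (percentage points) | False cases per group (1,175 × f) | Rate ratio | Exact power |
|---|---|---|---|
| 0 | 0 | 2.32/0.79 = 2.94 | 90.0% |
| 0.1 | 1.2 | 2.42/0.89 = 2.72 | 88.1% |
| 0.25 | 2.9 | 2.57/1.04 = 2.47 | 85.2% |
| 0.5 | 5.9 | 2.82/1.29 = 2.19 | 80.4% |
| 1.0 | 11.8 | 3.32/1.79 = 1.85 | 72.4% |

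The table shows what dilution would cost if it occurred. It does not estimate how much occurs.

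**The case against.** The best defence is that diagnosis is not computed from tick-boxes. Two blinded specialists judge each case and disagreements go to a board call (F21). Coordinators are trained on actual TRALI, ALI and TACO cases and in writing case summaries (F17), and the timeline they prepare is a natural place for a charted pneumonia or suspected aspiration. A pre-transfusion film read as pneumonia is time-stamped in the record. Note 17 is triggered by a mere possibility of sepsis. Note 5 can be read as a deliberate rule that fits F25's demand for a clear relationship to the alternate factor. Pre-existing ALI is excluded separately (F25 item 4).

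Most of this stands, and it rules out two stronger readings. A reader might infer that pneumonia and toxic inhalation go unmeasured; they do not, because several channels can carry them. A reader might also infer that TRALI will be misclassified as free of other causes. That would require every channel to miss the factor and no other recorded factor to be present, and nothing in the protocol shows how often that happens.

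What the defence does not remove is the lack of uniformity. Unprompted narrative varies between coordinators and centres, discharge codes cannot establish the temporal relationship F25 asks for, and Note 5 gives the panel an explicit negative where the chart holds a suspicion. F25 leaves the weight of that suspicion to the panel; the form partly settles it beforehand.

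**Conclusion.** The point holds as a mismatch between form and criteria. Two of five direct factors have no structured, dated item, and aspiration is coded so that suspicion reads as absence. These factors may be under-recorded, which may push the planned with/without split, and Canadian TRALI versus possible TRALI, toward the class without risk factors.

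The effect on that split cannot be sized from the protocol. In the single-hospital record review used for planning, 3 or 4 of 7 cases had other risk factors (Appendix A and Table 2 differ). Applied to the 40 expected cases this gives 40 × 3/7 = 17 to 40 × 4/7 = 23. That range covers every risk factor, not the three at issue, so it is no estimate of cases that would change class.

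For the primary comparison, a reader might infer an inflated difference between groups. The documents do not support that. Radiology, triage and panel reviews are blinded to antibody status (F3, F5, F21), so error should be non-differential and the consequence is dilution. The equal-addition illustration further assumes that these alternate causes are about equally common among recipients in both groups. This is a worthwhile correction to the form and does not undermine the primary analysis.

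**What to change.** In Appendix G, Section F, add two rows with start and resolve dates, as items 1 to 21 already have: pneumonia (charted or on the radiology report before the reaction) and toxic inhalation before the reaction. Change Note 5 so that aspiration is recorded as witnessed, suspected, no or not recorded, and show that grade to the panel. The panel then judges the weight of a suspicion, and the with/without split can be tabulated with suspected aspiration counted either way.

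The cost is two rows, one revised note and slightly more abstraction time per chart, in about 311 charts that Table-4 already schedules for detailed review. No diagnostic criterion in F25 changes.
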